### 3.6.1.2 Progression-Free Survival

The non-parametric Kaplan-Meier method will be used to estimate the PFS curve in each treatment group. The treatment difference in PFS will be assessed by the stratified log-rank test. A stratified Cox proportional hazard model with Efron's method of tie handling will be used to assess the magnitude of the treatment difference (ie, HR) between the treatment arms. The HR and its 95% CI from the stratified Cox model with a single treatment covariate will be reported. The stratification factors used for randomization (Section 6.3.2 of the protocol) will be applied to both the stratified log-rank test and the stratified Cox model.

Since disease progression is assessed periodically, PD can occur any time in the time interval between the last assessment where PD was not documented and the assessment when PD is documented. The true date of disease progression will be approximated by the earlier of the date of the first assessment at which PD is objectively documented per RECIST 1.1 by BICR and the date of death. Death is always considered a PD event. Surgical subjects (i.e., those who undergo oncologic surgeries with curative intent) will be followed to the disease recurrence after the surgery for PFS analysis.

For the primary analysis, any participant who experiences an event (PD or death) immediately after 2 or more missed disease assessments will be censored at the last disease assessment prior to the missed visits. In addition, any participant who initiates new anticancer therapy prior to documented progression will be censored at the last disease assessment prior to the initiation of new anticancer therapy. Participants who do not start new anticancer therapy and who do not experience an event will be censored at the last disease assessment. If a participant meets multiple criteria for censoring, the censoring criterion that occurs earliest will be applied.

In order to evaluate the robustness of the PFS endpoint per RECIST 1.1 by BICR, 2 sensitivity analyses with different sets of censoring rules will be performed. The first sensitivity analysis follows the intention-to-treat principle. That is, PDs/deaths are counted as events regardless of missed study visits or initiation of new anticancer therapy. The second sensitivity analysis considers initiation of new anticancer treatment or discontinuation of treatment due to reasons other than complete response, whichever occurs later, to be a PD event for participants without documented PD or death. If a participant meets multiple criteria for censoring, the censoring criterion that occurs earliest will be applied. The censoring rules for the primary and sensitivity analyses are summarized in [Table 1](#).

Table 1 Censoring Rules for Primary and Sensitivity Analyses of PFS

Situation	Primary Analysis	Sensitivity Analysis 1	Sensitivity Analysis 2
PD or death documented after $\leq 1$ missed disease assessment, and before new anticancer therapy, if any	Progressed at date of documented PD or death	Progressed at date of documented PD or death	Progressed at date of documented PD or death
PD or death documented immediately after $\geq 2$ consecutive missed disease assessments, or after new anticancer therapy	Censored at last disease assessment prior to the earlier date of $\geq 2$ consecutive missed disease assessment and new anticancer therapy, if any	Progressed at date of documented PD or death	Progressed at date of documented PD or death
No PD and no death; and new anticancer treatment is not initiated	Censored at last disease assessment	Censored at last disease assessment	Progressed at treatment discontinuation due to reasons other than complete response; otherwise censored at last disease assessment if still on-study treatment or completed study treatment
No PD and no death; new anticancer treatment is initiated	Censored at last disease assessment before new anticancer treatment	Censored at last disease assessment	Progressed at date of new anticancer treatment
PD=progressive disease; PFS=progression-free survival.			

The proportional hazards assumption on PFS may be examined using the same approach as OS, and supportive analyses may be conducted when the proportional hazard assumption is violated: for example, using the Restricted Mean Survival Time method (Finkelstein DM, 1986 [Finkelstein, D. M. 1986]).

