#### 3.7.1 Efficacy Interim Analyses

One IA is planned in addition to the FA for this study. For the IA and FA, all randomized participants will be included. Results of the IA will be reviewed by the eDMC. Details of the boundaries for establishing statistical significance with regard to efficacy are discussed further in Section 3.8.

The analyses planned, endpoints evaluated, and drivers of timing are summarized in [Table 8](#).

Table 8      Summary of Interim and Final Analyses Strategy

Analyses	Key Endpoints	Timing	Estimated Time after First Participant Randomized	Primary Purpose of Analysis
IA	OS (PFS and ORR if OS is rejected)	Both ~309 OS events have been observed and ~ 10 months after last participant randomized	~ 21 months	

• Interim OS analysis

• Final PFS and ORR analysis

FA	OS	Both ~386 OS events have been observed and ~ 12 months after IA	~ 33 months	

• Final OS analysis

Abbreviations: FA=final analysis; IA=interim analysis; ORR=objective response rate; OS=overall survival; PFS=progression-free survival.

Note that for FA, if the OS events accrual is slower than expected and the final targeted OS events cannot be reached by ~33 months after the first participant randomized, the Sponsor may conduct the analysis with up to additional ~4 months of follow-up, or the specified number of events is observed, whichever occurs first.

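### Does PFS sensitivity analysis 2 need rewriting because of how it dates the start of new anticancer therapy?

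*SAP*

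**What the plan says.** SAP section 3.6.1.2 and its Table 1 define three ways of handling PFS.

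- **Primary analysis:** "any participant who initiates new anticancer therapy prior to documented progression will be censored at the last disease assessment" before that therapy.
- **Sensitivity analysis 1:** "PDs/deaths are counted as events regardless of missed study visits or initiation of new anticancer therapy".
- **Sensitivity analysis 2:** the later of new anticancer therapy and discontinuation for reasons other than complete response is taken as progression, but only where neither progression nor death is documented ("whichever occurs later, to be a PD event for participants without documented PD or death").

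Table 1 separates progression or death that comes after at most one missed assessment "and before new anticancer therapy, if any" (row 1) from "PD or death documented immediately after" two or more missed assessments, or after new therapy (row 2). In both rows, sensitivity analysis 2 uses the documented progression or death date, as sensitivity analysis 1 does. Row 3 (no event, no new therapy) puts the event at discontinuation for reasons other than complete response. Row 4 (no event, new therapy started) reads "Progressed at date of new anticancer treatment", with no condition on when study treatment stopped.

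After the definition comes a tie-break: "If a participant meets multiple criteria for censoring, the censoring criterion that occurs earliest will be applied". Section 3.7.1, Table 8, lists "Final PFS and ORR analysis" as a purpose of the interim analysis, so PFS is analysed at one data cut.

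**The concern.** Two features look wrong.

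The first is an odd ordering. Suppose two participants both start new therapy at month 3. One dies at month 9 and has an event at month 9. The other is alive without progression at the cutoff and has an event at month 3. The worse course is credited with the longer PFS. Sensitivity analysis 2 is also the only one of the three rules that can count a switch as failure, yet it does so only when nothing is documented later. It therefore resembles sensitivity analysis 1 closely and may say little about the primary censoring rule in an open-label trial.

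The second is a mismatch between text and table. If new therapy starts before discontinuation, the sentence dates the event at discontinuation and row 4 dates it at new therapy. The tie-break concerns censoring criteria. Here both dates are event dates, so it does not decide between them, and two programmers could derive different datasets.

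What would be at stake is how informative and reproducible one supportive analysis is.

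**Working it through.** **1. Text and table side by side for sensitivity analysis 2**

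| Course by the cutoff | Text | Table 1 |
|---|---|---|
| New therapy, then documented progression or death | documented date | documented date (row 2) |
| Discontinuation (not for CR), then new therapy; no event | new therapy | new therapy (row 4) |
| Discontinuation (not for CR) only; no event | discontinuation | discontinuation (row 3) |
| New therapy month 3, discontinuation (not for CR) month 4.5; no event | month 4.5 | month 3 (row 4) |

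Only the last line conflicts. The first shows that the odd ordering is not a contradiction: the text limits imputation to participants without a documented event, and the table does the same.

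**2. The plan's own PFS figures**

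Inputs: 419 events, HR 0.65 and one-sided alpha 0.0125 (sections 3.8.2 and 3.9).

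Power = Φ(½·√419·|ln 0.65| − 2.2414) = Φ(4.409 − 2.241) = 0.985, against 0.9850 in Table 10. Sensitivity analysis 2 plays no part in this figure.

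**3. How many participants can be affected**

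Sensitivity analyses 1 and 2 have the same entries in rows 1 and 2, so they can differ only for participants without documented progression or death. At the projection this is at most 432 − 419 = 13 (13/432 = 3.0%).

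To check the projection, I used the section 3.9 inputs: control median 2 months, HR 0.65, 5% annual dropout and 216 per arm. I assumed follow-up uniform over 10 to 22 months. With λ the event hazard, η = −ln(0.95)/12 = 0.00427 and S = λ + η:

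P(event) = (λ/S)·[1 − (e^(−10S) − e^(−22S))/(12S)]

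- Control: λ = 0.3466, P = 0.981, giving 211.9 events.
- Experimental: λ = 0.2253, P = 0.948, giving 204.7 events.
- Total: 416.6 events, 8.9 still event-free and 432 − 416.6 − 8.9 = 6.5 dropouts.

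This is close to 419. If a half-rate enrolment ramp-up over the first 2 months is assumed instead, the count at month 21 is about 413, which raises the ceiling to 19 (4.4%).

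With no dropout the first model gives 423 events, so 419 leaves about 4 participants for early censoring of any kind. Censoring switchers at 1.5% in each arm gives 416 primary events, and at 3% it gives 410. The scenarios with about 13 switchers below are therefore already generous.

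**4. Would counting every switch as failure be better?**

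The plan gives no switching rates, so these are assumptions. Simulated hazard ratios, true value 0.65. Mechanism A: participants switch at true failure, before central review records it, with later progression or death at medians of 2 to 10.7 months. Mechanism B: participants switch at a random time before failure, and the failure is still documented.

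| Switching, control/experimental | As written, A | As written, B | Failure at switch, A | Failure at switch, B |
|---|---|---|---|---|
| 3%/3% | 0.656–0.662 | 0.650 | about 0.65 | 0.652 |
| 5%/1% | 0.675–0.686 | 0.652 | about 0.65 | 0.641 |
| 1%/5% | 0.631–0.638 | 0.652 | about 0.65 | 0.667 |

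At 1.5%/1.5%, the only rate that roughly fits 419 events, the rule as written gives 0.65–0.66 and failure at switch gives 0.65. Under A the alternative is right by construction. Under B the written rule is the closer one. Which is better depends on why participants switch, and the plan cannot know that in advance.

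**The case for a change.** The strongest case for a change is that it is cheap: one sentence and one split table row would make sensitivity analysis 2 a clean failure-at-switch analysis and would remove the conflict with row 4. Under the assumed patterns, 52–99% of switchers would carry the later documented date, so few switches would count as failures in the analysis that appears designed to count them.

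Part of this stands. The sentence and row 4 do disagree for one ordering, and sensitivity analysis 2 will indeed sit close to sensitivity analysis 1.

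The rest does not carry a change.

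- The plan never presents this as a failure-at-switch analysis. It keeps the defined endpoint when observed and imputes failure for unresolved participants. Overriding a documented progression or death with a switch date changes what is estimated.
- The proposed rule would leave row 3 with the same dependence on later events, so the supposed defect would survive for discontinuation.
- With 419/432 = 97% of participants projected to have an event, any alternative rule will nearly duplicate the others.
- Much heavier switching would matter more, but it does not fit the plan's projection and does not point one way. At 10%/30%, primary events fall to about 338, and under mechanism B failure at switch gives 0.75 against 0.66 as written. At 30%/10% with switching at failure (cutoff month 21, control median 5.5 months after the switch), the written rule gives about 0.82 against 0.65.

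**Conclusion.** No change follows. The different dating of switchers with and without a later event is a fair trade-off: it follows from respecting documented events and imputing only where none exists, text and table agree on it, and the alternative is a different analysis with no dependable gain.

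The mismatch between the sentence and row 4 is a clerical slip. It arises only if new anticancer therapy precedes discontinuation for reasons other than complete response and neither progression nor death is documented. That subset is unsized and lies within the at most 13 of 432 participants at the projected 419 events. An analyst working from Table 1 has an unconditional entry to follow, and either date gives a usable result.

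The size rests on the plan's PFS projection holding and on assumed switching patterns. Discontinuation was not modelled. What does not depend on those assumptions is that sensitivity analysis 2 carries no alpha and no power statement. The primary PFS rule, its single test and the 0.985 power stay as they are under either reading.

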### 3.6.1.3 Objective Response Rate

The stratified M&N method will be used for the comparison of ORR between 2 treatment groups [Miettinen, O. and Nurminen, M. 1985]. The difference in ORR and its 95% CI from the stratified M&N method with strata weighting by sample size will be reported. The stratification factors used for randomization (see Section 6.3.2 of the protocol) will be applied to the analysis.

The point estimate of ORR will be provided by treatment group, together with 95% CI using exact binomial method proposed by Clopper and Pearson [Clopper, C. J. and Pearson, E. S. 1934].

### 3.6.1.4 Duration of Response

If sample size permits, DOR will be summarized descriptively using Kaplan-Meier medians and quartiles. Only the subset of participants who show a confirmed complete response or partial response will be included in this analysis. CCI

CCI

Table 2 Censoring Rules for DOR

CCI

### 3.6.1.5 Analysis Strategy for Key Efficacy Variables

A summary of the primary analysis strategy for the key efficacy endpoints is provided in [Table 3](#).

Table 3 Analysis Strategy for Key Efficacy Variables

Endpoint/Variable	Statistical Method	Analysis Population	Missing Data Approach
Primary Analysis			
OS	Testing: stratified log-rank test Estimation: Stratified Cox model with Efron's tie handling method	ITT	Censored at the date participant last known to be alive
Key Secondary Analyses			
PFS per RECIST 1.1 by BICR	Testing: stratified log-rank test Estimation: Stratified Cox model with Efron's tie handling method	ITT	Censored according to rules in Table 1
ORR per RECIST 1.1 by BICR	Testing and estimation: stratified M&N method	ITT	Participants with missing data are considered non-responders
Abbreviations: BICR=blinded independent central review; ITT=intent-to-treat; M&N=Miettinen & Nurminen; ORR=objective response rate; OS=overall survival; PFS=progression-free survival; RECIST 1.1=Response Evaluation Criteria in Solid Tumors.			

### 3.6.2 Statistical Methods for Safety Analyses

Safety and tolerability will be assessed by clinical review of all relevant parameters including AEs and laboratory tests.

The analysis of safety results will follow a tiered approach ([Table 4](#)). The tiers differ with respect to the analyses that will be performed. Adverse events (specific terms as well as system organ class terms) and events that meet predefined limits of change in laboratory and vital signs are either prespecified as “Tier 1” endpoints or will be classified as belonging to “Tier 2” or “Tier 3” based on the observed proportion of participants with events.

#### Tier 1 Events

Safety parameters or AEs of special interest that are identified a priori constitute “Tier 1” safety endpoints that will be subject to inferential testing for statistical significance. There are no Tier 1 events for this protocol. Adverse events that are immune-mediated or potentially immune-

mediated are well documented and will be evaluated separately; however, these events have been characterized consistently throughout the pembrolizumab clinical development program, and determination of statistical significance is not expected to add value to the safety evaluation. The coformulated MK-4280A has not been found to be associated with any new safety signals. Finally, there are no known AEs associated with participants with CRC for which determination of a p-value is expected to impact the safety assessment.

### **Tier 2 Events**

Tier 2 parameters will be assessed via point estimates with 95% CIs provided for differences in the proportion of participants with events using the M&N method, an unconditional, asymptotic method [Miettinen, O. and Nurminen, M. 1985].

Membership in Tier 2 requires that at least 10% of participants in any treatment group exhibit the event; all other AEs and predefined limits of change will belong to Tier 3. The threshold of at least 10% of participants was chosen for Tier 2 events because the population enrolled in this study is in critical condition and usually experiences various AEs of similar types regardless of treatment; events reported less frequently than 10% of participants would obscure the assessment of the overall safety profile and add little to the interpretation of potentially meaningful treatment differences. In addition, Grade 3 to 5 AEs ( $\geq 5\%$  of participants in 1 of the treatment groups) and SAEs ( $\geq 5\%$  of participants in 1 of the treatment groups) will be considered Tier 2 endpoints. Because many 95% CIs may be provided without adjustment for multiplicity, the CIs should be regarded as a helpful descriptive measure to be used in safety review, not as a formal method for assessing the statistical significance of the between-group differences.

### **Tier 3 Events**

Safety endpoints that are not Tier 1 or 2 events are considered Tier 3 events. The broad AE categories consisting of the proportion of participants with any AE, a drug-related AE, a serious AE, an AE which is both drug-related and serious, a Grade 3-5 AE, a drug-related Grade 3-5 AE, and discontinuation due to an AE will be considered Tier 3 endpoints. Only point estimates by treatment group are provided for Tier 3 safety parameters.

### **Continuous Safety Measures**

For continuous measures such as changes from baseline in laboratory parameters, summary statistics for baseline, on-treatment, and change from baseline values will be provided by treatment group in table format.

Table 4 Analysis Strategy for Safety Parameters

Safety Tier	Safety Endpoint	95% CI for Treatment Comparison	Descriptive Statistics
Tier 2	Grade 3-5 AE (incidence $\geq 5\%$ of participants in one of the treatment groups)	X	X
	Serious AE (incidence $\geq 5\%$ of participants in one of the treatment groups)	X	X
	AEs (incidence $\geq 10\%$ of participants in one of the treatment groups)	X	X
Tier 3	Any AE		X
	Any Grade 3-5 AE		X
	Any Serious AE		X
	Any Drug-Related AE		X
	Any Serious and Drug-Related AE		X
	Any Grade 3-5 and Drug-Related AE		X
	Discontinuation due to AE		X
	Death		X
	Specific AEs, system organ class (incidence $< 10\%$ of participants in all of the treatment groups)		X
	Change from Baseline Results (laboratory toxicity shift)		X
AE=adverse events; CI=confidence interval.			

Frequency of AE by time period from first dose (e.g., 0-3, 3-6, 6-12 months) may also be provided. In each time interval, the denominator is the number of participants at risk for the event during the particular time period, defined as participants who are event-free up until the start of the interval.

To properly account for the potential difference in follow-up time between the study arms, AE incidence adjusted for treatment exposure analyses may be performed as appropriate.

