#### 3.5.2 Safety Analysis Populations

Safety Analyses will be conducted in the APaT population, which consists of all randomized participants who received at least one dose of study treatment. Participants will be included in the treatment group corresponding to the study treatment they actually received for the analysis of safety data using the APaT population. This will be the treatment group to which they are randomized except for participants who take incorrect study treatment for the entire treatment period; such participants will be included in the treatment group corresponding to the study treatment actually received.

At least one laboratory or vital sign measurement obtained after at least one dose of study treatment is required for inclusion in the analysis of the respective safety parameter. To assess change from baseline, a baseline measurement is also required.

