### 3.9 Sample Size and Power Calculations

The study will randomize 432 participants in a 1:1 ratio into the MK-4280A arm (Arm A) and the standard of care arm (Arm B). OS is the primary endpoint for the study, with PFS and ORR as the key secondary endpoints.

For the OS endpoint, based on a target number of 386 events and 1 IA at approximately 80% of the target number of events, the study has approximately 93.5% power to detect a HR of 0.7 at the initially allocated  $\alpha=0.025$  (1-sided).

For the PFS endpoint, based on a target number of 419 events at the IA (final PFS analysis), the study has approximately 99% power to detect a HR of 0.65 at the reallocated  $\alpha=0.0125$  (1-sided) if only OS hypothesis is rejected.

Based on the 432 participants with at least approximately 10 months of follow-up, the power of the ORR testing at the reallocated  $\alpha=0.0125$  (1-sided) if only OS hypothesis rejected is approximately 97% to detect a 10-percentage point difference between an underlying 2% ORR in the control arm (Arm B) and a 12% ORR in the experimental arm (Arm A).

Note that the above OS and PFS power calculations are based on a constant HR assumption.

[figure not shown]
Based on CORRECT, RE COURSE, and SUNLIGHT studies (Section 4.2.1.1 of protocol), the above sample size and power calculations for OS and PFS assume the following:

- OS follows an exponential distribution with a median of 7.5 months for the control group.
- PFS follows an exponential distribution with a median of 2 months for the control group.
- Enrollment period of 12 months with enrollment ramp-up over first 2 months.
- An annual dropout rate of 2% and 5% for OS and PFS, respectively
- A follow-up period of 22 and 10 months and for OS and PFS, respectively, after the last participant is randomized.

The sample size and power calculations were performed using R (“gsDesign” package).

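### The denominator for AE frequency by time period requires only that participants be event-free, so read literally it keeps the dead and those out of follow-up and understates later-interval frequency

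*SAP*

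**What the plan says.** SAP Section 3.6.2, in the text that follows Table 4, offers an additional safety display: "Frequency of AE by time period from first dose (e.g., 0-3, 3-6, 6-12 months) may also be provided". The base for each interval's percentage is then described in these terms: "at risk for the event during the particular time period, defined as participants who are event-free up until the start of the interval".

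The next paragraph adds a separate option: "To properly account for the potential difference in follow-up time between the study arms, AE incidence adjusted for treatment exposure analyses may be performed". This too is left to discretion. It is not said to be done by interval, and it does not alter the denominator above.

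The safety population (Section 3.5.2) supplies no further condition. It is the APaT population, "which consists of all randomized participants who received at least one dose of study treatment".

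**The concern.** The sentence uses the right term, at risk, but then defines it by one condition: no event before the interval starts. A participant who died or left AE follow-up earlier without the event meets that condition and counts in every later denominator, although no AE can be recorded for them.

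Two consequences follow if the rule is programmed as written:

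- Later-interval frequencies fall in both arms because people have died or left observation. A reader could take this as AEs becoming rarer with time on study, which is the very question the table is meant to answer.
- If survival or follow-up differs by arm, the dilution differs too. An identical AE hazard then looks higher in the arm whose participants stay longer.

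The expected mortality makes this more than a formality here: the planned control OS median is 7.5 months, and the suggested intervals run to month 12.

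**Working it through.** **Inputs from the SAP (Section 3.9).** "OS follows an exponential distribution with a median of 7.5 months for the control group". The OS HR under the alternative is 0.7. There are 432 participants randomized 1:1, so 216 per arm. The SAP gives no figure for the interval table itself.

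**Check of the OS inputs.** Lan-DeMets O'Brien-Fleming-type spending at 309/386 events, one-sided 0.025, gives Z bounds of 2.2495 and 2.0251 and power of 93.46% at HR 0.7. Table 9 states 2.2504, 2.0249 and 93.50%. The OS figures reproduce to within rounding and are not in dispute.

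**Deaths on those assumptions**
- Control: by month 3, 1 − exp(−ln2 × 3/7.5) = 24%; by month 6, 1 − exp(−ln2 × 6/7.5) = 43%.
- MK-4280A: by month 3, 1 − exp(−0.7 × ln2 × 3/7.5) = 18%; by month 6, 1 − exp(−0.7 × ln2 × 6/7.5) = 32%.

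**Assumptions not in the SAP.** First-AE hazard h = 0.1 per month, constant, equal in both arms and independent of death; AE observation until death; all 216 per arm treated.

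**Formulas.** Let l be the hazard of leaving observation: ln2/7.5 = 0.0924 for control and 0.7 × ln2/7.5 = 0.0647 for MK-4280A. The proportion with a recorded first event by time t is

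F(t) = h/(h + l) × [1 − exp(−(h + l)t)].

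For an interval from a to b:
- new events: 216 × [F(b) − F(a)]
- denominator as written: 216 × [1 − F(a)]
- true at-risk denominator: 216 × exp(−(h + l)a)

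| Interval | Arm | New events | Denominator as written | True at-risk | Frequency as written | Frequency, true at-risk |
|---|---|---|---|---|---|---|
| 3-6 months | Control | 27.64 | 166.77 | 121.27 | 16.6% | 22.8% |
| 3-6 months | MK-4280A | 31.20 | 164.87 | 131.79 | 18.9% | 23.7% |
| 6-12 months | Control | 24.23 | 139.13 | 68.09 | 17.4% | 35.6% |
| 6-12 months | MK-4280A | 30.65 | 133.67 | 80.41 | 22.9% | 38.1% |

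**Reading the table**
- At month 6 the as-written denominator includes 139.1 − 68.1 = 71.0 dead control participants (51%) and 133.7 − 80.4 = 53.3 dead MK-4280A participants (40%).
- The 0-3 month interval is unaffected (22.8% and 23.7%). With a constant hazard, 3-6 months should repeat those values, and on the true at-risk set it does. As written, control drops to 16.6%, a decline produced by the denominator alone.
- The between-arm ratio (MK-4280A over control) as written is 1.14 for 3-6 months and 1.32 for 6-12 months, against 1.04 and 1.07 on the true at-risk set.

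**Sensitivity**
- Hazards of 0.05 to 0.2 per month give as-written ratios of 1.14-1.15 (3-6 months) and 1.29-1.37 (6-12 months).
- At h = 0.05 the 6-12 month frequencies are 10.8% versus 13.9% as written, against 20.2% versus 21.7%.
- At HR = 1 both arms take the control values: ratio 1.00, but 17.4% in place of 35.6% for 6-12 months.
- If AE observation ended at progression, the as-written ratios at h = 0.1 would be 1.72 and 2.81 (l = ln2/2 for control and 0.65 × ln2/2 for MK-4280A, from the SAP's PFS assumptions). This SAP does not state the AE window, so this is only an upper bound for illustration.

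**The case against.** The strongest reply is that at risk already means alive and observed. On that view the definition clause only removes participants who have had the event, so that first events are counted, and a competent programmer would use the ordinary risk set. That is plausible, and it means the wording does not prove the table will be wrong. But the sentence goes on to say what the term means, and that definition omits survival and observation. Two programmers could follow it in good faith and produce very different tables.

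Second, the length of AE follow-up is normally set in the protocol, so its absence here is no fault. That stands, and the remedy can simply refer to that period. It does not excuse a stated denominator that ignores whether the participant is in the period at all.

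Third, the exposure-adjusted analysis already deals with unequal follow-up. It would help, but it is equally optional, is not described per interval and leaves this denominator as it is.

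Fourth, the figures depend on an assumed AE hazard, and the between-arm distortion depends on a real survival difference. Both are true. In absolute terms the added gap is modest: for 6-12 months at h = 0.1, 22.9 − 17.4 = 5.5 points as written against 38.1 − 35.6 = 2.5 points. The understatement within each arm is larger, and it needs no treatment effect.

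Finally, nothing confirmatory depends on the table. It is optional, is not listed in Table 4 and carries no CI or test. That settles the severity, not whether the definition is right.

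**Conclusion.** The concern holds, as a minor point. The stated definition of at risk is incomplete; followed literally, it puts participants who have died or left AE follow-up into later-interval denominators. In the illustration this roughly halves the 6-12 month frequency in control (35.6% to 17.4%) and lowers it from 38.1% to 22.9% on MK-4280A. It also raises the between-arm ratio from 1.07 to 1.32 when the true AE hazard is equal.

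The death proportions rest on the SAP's planning assumptions. The AE frequencies also rest on an assumed constant hazard and on AE observation until death. The direction of the error does not depend on the hazard chosen. The between-arm part disappears if survival and follow-up are the same in both arms. No hypothesis test, alpha, power figure, or Tier 2 or Tier 3 summary is affected.

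**What to change.** In Section 3.6.2, define the interval denominator as APaT participants who, at the start of the interval, have not had the event, are alive and are still within the AE reporting period. Show that number for each interval and arm.

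Participants also leave during an interval, so some imbalance remains after this change. At h = 0.1 the ratios are 1.04 and 1.07 with observation until death, rising to 1.26 for 6-12 months if observation ended at progression. Giving the exposure-adjusted event rate for each interval alongside would address this. It is a useful addition, but the correction to the definition does not depend on it.

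The cost is one sentence in the SAP, one programming filter and, if the rate is added, one column. The trade-off is smaller and less precise denominators in the late intervals: in the illustration, about 68 and 80 at month 6 in place of 139 and 134.
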